XIV. CONFIDENTIALITY.....	17
XV. REFERENCES.....	18

Vapotherm, Inc
New HVNI Device Design Efficacy in Relieving Dyspnea
Confidential

Glossary of Definitions and Terms

High Flow Nasal Cannula (HFNC): Nasal cannula system that delivers flow rates of respiratory gas meeting or exceeding a patient's normal spontaneous inspiratory flow demand. HFNC systems must maintain adequate heating and humidification of the delivered gas to protect the airway tissues from dryness.

High Velocity Nasal Insufflation (HVNI): a system consisting of heated and humidified gas mixtures of varying FiO_2 delivered to a patient using a small-bore nasal cannula, at generally high flow rates imparted with increased velocity as compared to other standard large-bore cannulae. The flow rates of respiratory gas generally exceed a patient's normal spontaneous inspiratory flow demand. HVNI systems must maintain adequate heating and humidification of the delivered gas to protect the nasal tissues from dryness and provide patient comfort.

Non-Invasive Positive Pressure Ventilation (NIPPV): Breathing assist where a mask is strapped tightly to a patient's face and bi-level positive airway pressure is administered at an established frequency to support patient ventilation. NIPPV may also refer to Continuous Positive Airway Pressure (CPAP).

Intubation: The placement of an endotracheal tube to facilitate respiratory support and provide airway protection.

Respiratory Failure: The inability to maintain sufficient arterial blood oxygen saturation and/or retention of carbon dioxide levels during unassisted spontaneous breathing.

Pulmonary Rehabilitation: Exercise regimen for patients with compromised cardio-pulmonary function designed to improve pulmonary parameters.

Pulse Oximetry Reading (SpO_2): Indirect measure of a patient's arterial blood oxygen saturation using pulse oximetry technology that utilizes oxygen/hemoglobin concentrations.

Resting SpO_2 : SpO_2 value the patient demonstrated at rest, while sitting upright and connected to the pulse oximetry monitor prior to the start of the study session. This value will be patient specific and reflect oxygen saturation.

Desaturation SpO_2 : The SpO_2 value considered to be the point of desaturation where the value drops below a specified threshold. This value is based on the desaturation requirement for reimbursement of oxygen therapy.

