5. Known contraindication to perform steps of the protocol
6. Absence of spontaneous respiration or known contraindication to HVNI
7. Inability to use nasal and/or HVNI therapy
8. Agitation or uncooperativeness
9. Determined by the clinician to be sufficiently unstable or unsuitable for this study

IV. Study Design

This study is an efficacy study, which will be performed as a prospective, order-randomized crossover design trial to evaluate the ability of the new HVT2.0 HVNI device design to effect ventilation and physiological responses relative to the Precision Flow HVNI device design. Patients deemed by investigators to meet inclusion criteria will undergo the study procedures for both arms of the crossover design. Patients are expected to complete the study in one session. After each of the study arms, both clinicians and patients will complete perception score assessments as measured by continuous Visual Analogue Scales (VAS). The clinical management of patients will otherwise remain unchanged based on-site standards of care.

This study has two phases. Each phase of the study will correspond to a different device design. In phase 1, the patients will be order randomized to the Precision Flow (Control) design phase, **or** to the new HVT2.0 design (Testing) phase. In phase-2 the order will change.

- Phase 1 – Precision Flow (Control) or HVT2.0 (Testing) (order randomized)
- Phase 2 – Precision Flow (Control) or HVT2.0 (Testing) (order randomized)

This study design will focus on four distinct segments for each phase: (1) baseline characterization, (2) therapy acclimatization, (3) therapeutic characterization, and (4) Continuous VAS for both

Vapotherm, Inc

New HVNI Device Design Efficacy in Relieving Dyspnea

Confidential

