Upon enrollment, appropriate study data will be collected (see below under Data Collection), including patient demographics (e.g. age, gender, ethnicity, race), anthropometrics (e.g. weight, height, BMI, and applicable medical history) including a detailed focus on the patient's current respiratory status (LTOT user, positive-airway pressure therapy [NIPPV] user, current respiratory therapy). Subjects will be managed by routine care while study data is captured as shown in the timeline below (Table 1). All decision making with regard to patient participation will be made in conjunction with appropriate medical professionals per standard practice at the trial site. Time required from screening to the end of the study, is estimated to be 1.65 hours in duration.

[figure not shown]

Figure 1. Framework of the clinical study procedures discussed within this protocol. Each Phase is designated by a Precision Flow or HVT2.0 design.

Vapotherm, Inc

New HVNI Device Design Efficacy in Relieving Dyspnea

Confidential

Phase 1 – Precision Flow (Control) or HVT2.0 (Test) design (order randomized)

This test session is represented by Phase 1 in Figure 1, where the patient is placed on HVNI device therapy with the order-randomized conventional or new device design. Phase 1 will follow four distinct segments: (1) baseline characterization, (2) therapy acclimatization, (3) therapeutic characterization, (4) patient and clinician assessment scores.

Baseline Characterization will be performed just prior to the therapy acclimatization segment of this Phase. If, for any reason, the clinician does not deem the patient appropriate for the study, per inclusion/exclusion criteria, they may stop procedures during baseline characterization. The patient may be sitting or lying down in a comfortable environment. The patient will be set up for study testing with appropriate data recording devices. While subject is at rest, the following data will be collected (see Table 1): RR, HR, BP, SpO₂, TcPCO₂ and RPD (Modified Borg scale 0-10). For the RPD, the clinician will record patient scores. The patient may or may not be on HVNI therapy at this the time the RPD is completed. The Phase 1, baseline characterization will include recording data while the patient is in an uncompromised state (e.g. ON current oxygen therapy, if applicable).

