Therapy acclimatization (5 – 10 minutes) will be performed immediately after the baseline characterization segment is complete, and in accordance with site standard of care practices to maintain patient safety. The patient will be fitted with an appropriately-sized Prosoft dual-pronged nasal cannula, which is not to exceed 50% occlusion of the nares. Patient will be notified of best practice for the therapy and investigators will record whether patients choose to keep their mouths open or closed. The acclimatization segment is the interval during which HVNI is to be titrated to provide the patient the appropriate settings for effective HVNI therapy. After the final FiO₂/Flow settings are implemented and the patient is acclimatized the following data will be collected (see Table 1): RR, HR, BP, SpO₂, TcPCO₂ and RPD (Modified Borg scale 0-10). For the RPD, the clinician will record patient scores. Effective flow-is will be recorded. Therapy acclimatization is only necessary in Phase 1, as both devices used in this study will be operating on the same settings.

HVNI therapy provided by either Precision Flow or HVT2.0 will be initiated per settings identified below, after which settings will be titrated per standard practice for optimal effect. When patients are placed, the HVNI initial settings will be the following: FiO₂ = level approximating the patient's prior prescription (e.g. if by nasal cannula [NC], 1LPM NC = 24%, 2LPM NC = 28%, 3LPM NC = 32%, etc.), Flow = 15 L/min, and Temperature = 35 - 37°C. Patients will be fit with a Vapotherm adult nasal cannula that will be applied by a respiratory therapist or other clinician skilled in management of HVNI. The flowrate can be decreased or increased as rapidly as necessary to alleviate respiratory distress and optimize patient comfort. Targets should be to provide relief of perceived dyspnea at an HVNI flow rate between 20 to 35 L/min (up to 40L/min). Starting temperature will be between 35 to 37°C; if patients find the gas temperature to be uncomfortable, it can be lowered as necessary down to 33 C to enhance tolerance. The FiO₂ will be set initially to approximate the likely previous dosage (see above) to initially to assure adequate oxygenation, but this should be adjusted to maintain a PaO₂ > 88%.

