Baseline Characterization will be performed just prior to the therapy acclimatization segment of this Phase. If, for any reason, the clinician does not deem the patient appropriate for the study, per inclusion/exclusion criteria, they may stop procedures during baseline characterization. Sitting down in a comfortable environment, the patient will be setup and prepared for the testing with appropriate data recording devices. The patient will be ON current/home oxygen therapy at this time (if applicable). While the subject is at rest, the following data will be collected (see Table 1): RR, HR, BP, SpO₂, tcPCO₂ and RPD (Modified Borg scale 0-10). For the RPD, the clinician will record patient scores.

Therapeutic Characterization will be performed immediately after the baseline segment is completed in Phase 2 only. Once the respiratory therapist or other clinician skilled in management of HVNI deems that the HVNI settings are having a therapeutic effect, the following data will be collected (see Table 1): RR, HR, BP, SpO₂, TcPCO₂ and RPD (Modified Borg scale 0-10). For the RPD, the clinician will record patient scores.

Patient & Clinician Perception Assessments will be performed by the clinician or therapist performing this phase's testing procedures. Immediately following the completion of this phase, the continuous Visual Analogue Scale (VAS) will be completed for each of the five endpoints for clinician assessment and the two endpoints for patient assessment. For patient perception these endpoints include: (1) relief of symptoms, and (2) comfort/tolerance. For clinician perception these endpoints include: (1) technical/clinical difficulties, (2) patient comfort & tolerance, (3) ease of use, (4) monitoring & support for therapy, and (5) expected/perceived patient outcomes.

Vapotherm, Inc
New HVNI Device Design Efficacy in Relieving Dyspnea
Confidential

Upon completion of Phase 2, the study testing procedures will be deemed completed, and any final study data will be recorded at this time. At this time, the patient may resume current/home oxygen therapy.

Other Medical Care

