All other medical treatment will remain the purview of the attending physician and will be administered per hospital standards. This study is designed only to evaluate patients' ventilatory performance, oxygenation, and physiologic parameters while on HVNI with current and new device designs. It is assumed that ancillary interventions will follow common clinical practice guidelines and conventions. All treatments given to the subjects will be noted on appropriate CRFs.

Vapotherm, Inc
New HVNI Device Design Efficacy in Relieving Dyspnea
Confidential

VII. Data Collection

Table 1. Key study data and collection points for each Phase of the Study.

	Baseline Characterization	Therapy Acclimatization	Therapeutic Characterization	@ Study End
Patient History & Health	X			
Treatment: Flow & O2	X	X	X	
Physiologic Parameters	X	X	X	
Ventilation Parameters	X	X	X	
Clinician Perception Scores			X	X
Patient Perception Scores			X	X

Data collection during enrollment will include patient history, health, demographics, and current respiratory therapies. Patients' health history and background information will be recorded in Phase 1 only. For each segment of each phase, the following data will be recorded for comparison:

Physiologic Parameters

- SpO₂, HR, RR, BP

Ventilation Parameters

- RPD, TcCO₂

Primary Endpoint

- Modified Borg scale score(s) –Rated Perceived Dyspnea (RPD)

Secondary Endpoints

- Physiologic parameter(s) – SpO₂, HR, RR, BP
- Ventilation parameter(s) –TcCO₂

Tertiary Endpoints – Patient & Clinician Assessment

- Patient Assessment
 - Patient assessment of respiratory response to therapy, ranging from Insufficient to Excellent Response, as continuous VAS.
 - Patient assessment of comfort and tolerance of the therapy, ranging from Insufficient to Excellent as continuous VAS.
- Clinician Assessment
 - Clinician assessment of patient respiratory response to therapy, ranging from Insufficient to Excellent Response, as continuous VAS.
 - Clinician assessment of frequency of rain-out, interface slippage or other technical/clinical difficulties applying therapy, ranging from Never to Frequent as continuous VAS.

Vapotherm, Inc

New HVNI Device Design Efficacy in Relieving Dyspnea

Confidential

- Clinician assessment of patient comfort and tolerance of therapy, ranging from Insufficient to Excellent as continuous VAS.
- Clinician a of Simplicity of set-up and use, ranging from Complex to Setup and Use to Simple to Setup and Use, as continuous VAS.

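### Phase 1 set-up allows sitting or lying and Phase 2 set-up has the patient sitting, so posture can change along with the device and add avoidable noise to the paired comparison

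*Combined protocol and SAP*

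**What the plan says.** Section VI (Study Procedures) gives a separate set-up instruction for each phase. The Phase 1 Baseline Characterization reads: "The patient may be sitting or lying down in a comfortable environment". The Phase 2 Baseline Characterization reads: "Sitting down in a comfortable environment, the patient will be setup and prepared for the testing with appropriate data recording devices". On the Phase 2 on-device reading, the same section says: "Therapeutic Characterization will be performed immediately after the baseline segment is completed in Phase 2 only".

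Neither Therapeutic Characterization paragraph mentions posture. Table 1 in Section VII does not list it, and no section asks for it to be held constant or recorded.

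Section IV describes a "prospective, order-randomized crossover design trial" in which each phase is a different device. Section VII lists dyspnea (RPD), TcCO2, SpO2, heart rate, respiratory rate and blood pressure under this instruction: "For each segment of each phase, the following data will be recorded for comparison". Section VIII plans a Wilcoxon signed rank test, or a t-test if the data look normal, at the 0.05 level. It gives no period or sequence term.

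Two side points. The glossary entry for resting SpO2 specifies "while sitting upright and connected to the pulse oximetry monitor prior to the start of the study session". In the acclimatization segment, which exists only in Phase 1, "investigators will record whether patients choose to keep their mouths open or closed".

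**The concern.** Each patient is his or her own control, so whatever differs between the two phases besides the device enters that patient's device difference. Inpatients are eligible, and the text expressly permits lying in Phase 1. A patient who uses that option and is then seated for Phase 2 changes posture at the same moment as device. Breathlessness and gas exchange at rest can depend on posture, so the primary endpoint and several secondary endpoints are exposed.

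At stake is the precision of the device comparison. The objective in Section II is comparability, but Section VIII plans a test for a difference. Under such a test, extra noise makes a non-significant result likelier, and that result could be misread as evidence that the devices are comparable.

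**Working it through.** **Inputs from the documents (Section V).** Difference 2 Borg points; SD 3, taken here as the SD of the paired difference; alpha 0.05; power 90%; N=26, with up to 32 enrolled. The text does not state whether the test is one- or two-sided.

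**Reproducing the plan's figure.** A two-sided paired t-test with the noncentral t distribution gives 89.2% power at n=25 and 90.4% at n=26. The stated N=26 is reproduced.

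**Assumptions (not in the documents).** A share f of patients lie in Phase 1 and sit in Phase 2; the others keep one posture. Lying shifts RPD by s points. The posture at set-up persists to the therapeutic reading. The raw therapeutic scores of the two phases are compared.

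**Direction.** Take the difference as HVT2.0 minus Precision Flow. A patient who changes posture contributes +s if HVT2.0 came first and −s if Precision Flow came first. With equal orders the mean shift is zero, and the variance becomes 3² + f·s². With n1 and n2 patients in the two orders, bias = f·s·(n1 − n2)/N.

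**Worked cases at f = 0.5, equal orders.**
- s = 1: SD = √(9 + 0.5) = 3.08; power for a 2-point difference at N=26 is 88.9%; 27 patients are needed for 90%.
- s = 2: SD = √(9 + 2) = 3.32; power is 84.0%; 31 patients are needed for 90%.

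**Range over the assumptions (N=26).**

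| f | s | SD, equal orders | Power, equal orders | Bias at 16/10 = f·s·6/26 |
|---|---|---|---|---|
| 0.25 | 1 | 3.04 | 89.6% | 0.06 |
| 0.25 | 2 | 3.16 | 87.3% | 0.12 |
| 0.5 | 1 | 3.08 | 88.9% | 0.12 |
| 0.5 | 2 | 3.32 | 84.0% | 0.23 |
| 1 | 1 | 3.16 | 87.3% | 0.23 |
| 1 | 2 | 3.61 | 77.6% | 0.46 |

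The f = 1 rows are limiting cases in which every patient lies in Phase 1. The s = 2 rows assume a posture effect as large as the plan's whole clinically important difference.

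**How likely are unequal orders?** The documents state no allocation ratio or blocking. Under simple 1:1 randomization of 26 patients, a split of 16/10 or worse has a probability of about 33%.

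**What a period term would do.** It removes the mean shift and the bias from unequal orders. Patient-to-patient variation of f(1 − f)s² remains. At f = 0.5 and s = 2 that is 0.5 × 0.5 × 4 = 1, against f·s² = 2 without the term.

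**The case against.** The case against giving this much weight is good, and most of it stands.

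- **Baseline text only.** Both posture sentences govern baseline set-up. Persistence to the therapeutic reading is plausible, above all in Phase 2 where that reading follows directly, but it is not written. Phase 1 permits lying and does not require it.
- **Choice of comparison.** Aim 1 speaks of relief of dyspnea, and each phase has its own baseline RPD. If relief is analysed as change from that baseline, a posture held within the phase largely cancels. The documents do not settle which comparison is used.
- **Size.** Neither f nor s comes from the documents. A 1-point shift costs 1.5 percentage points of power. SD 3 is the top of the plan's range of 2 to 3. At SD 2, with f = 0.5 and s = 2, the inflated SD is √(4 + 2) = 2.45, still below the planned 3.

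Some stronger readings are tempting but not supported:

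- A reader might infer systematic bias toward one device. Posture follows phase, not device, and order is randomized, so the shift cancels on average.
- A reader might infer that the shift cannot be removed afterwards. A period-adjusted analysis removes its mean, though not the variation between patients.
- A reader might infer that posture is certainly unrecorded. Table 1 lists key data only, and the CRF is not among the documents.
- A reader might say that noise hurts the trial by widening an equivalence interval. Section VIII sets no margin and plans no such interval; under the planned test the noise works the other way.
- The glossary entry is not a conflicting instruction, because the endpoints, procedures and analysis do not use resting SpO2 as a named term. Mouth position is likewise a side point, since no text gives different mouth instructions by phase.

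What survives is that the plan states two different set-up rules for phases that are to be compared within patient, with no provision for holding or recording posture.

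**Conclusion.** The inconsistency is real, and its consequence is limited: extra variance in the paired difference, plus a small bias if the orders are unequal, because the planned test has no period term. If half the patients change posture, the change persists and raw scores are compared, the power loss runs from 1.5 points (s = 1) to 6.4 points (s = 2, an upper case). The corresponding bias at a 16/10 split is about 6% to 12% of the 2-point important difference (0.12/2 to 0.23/2). These power figures are for the paired t-test used in Section V, not for the Wilcoxon test. The effect is smaller if each phase's own baseline is subtracted.

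Severity: minor. Confidence is high that the two texts differ and low on the size of the effect.

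**What to change.** Reconcile the two set-up sentences in Section VI with one rule: the posture each patient takes at Phase 1 baseline, as comfortable for that patient, is kept for all readings in both phases where the patient's condition allows. Record posture, and mouth open or closed, at each reading in both phases. Flag any change, and show the primary comparison with and without the patients concerned.

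The cost is one sentence and two CRF fields, with no added procedure or patients. With posture held constant the added term is zero, and the stated N=26 with 90.4% power is unchanged.

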Aim #1: Primary Outcome. The primary endpoint is the patient's targeted relief of dyspnea, as measured by the modified Borg (rated perceived dyspnea [RPD]) for each device design tested.

Aim #2: Secondary Outcomes. The secondary endpoints evaluate the patient vital signs (heart rate [HR], respiratory rate [RR], blood pressure [BP]), arterial oxygen saturation (SpO₂), and PCO₂ as measured by a transcutaneous CO₂ device (TcPCO₂). These measurements will be compiled and compared for each device design tested.

Aim #3: Tertiary Outcomes. The tertiary endpoints evaluate the patient and clinician assessment scores. For the patient perception/satisfaction these include: (1) relief of symptoms, and (2) comfort/tolerance. For the clinician perceptions these include: (1) technical/clinical difficulties, (2) patient comfort & tolerance, (3) ease of use, (4) monitoring & support for therapy, and (5) expected/perceived patient outcomes.

The **endpoints** described will establish equivalence of outcomes between Precision Flow HVNI and HVT2.0 HVNI device design.

Vapotherm, Inc

New HVNI Device Design Efficacy in Relieving Dyspnea

Confidential

III. Subject Selection

Subjects will be identified through the use of patient medical records and recruited by study investigators. The study will take place in an inpatient or outpatient setting capable of supporting patients presenting with hypercapnic respiratory failure. Device testing during this study will be performed under the direct supervision of qualified healthcare professionals and appropriately trained study staff to maintain patient safety. The ~~test~~-study will evaluate patient dyspnea, vital signs, ventilation, and oxygenation for each device design tested. Initial patient contact will be made by study investigators. Participants may decide whether to enroll after being consented; furthermore, participants may choose to withdraw their consent at any point throughout the study.

Inclusion Criteria

1. Adults, 18 years or older
2. Demonstrated dyspnea at baseline, established by clinician OR patient assessment (see below)
 - a. Borg Rated Perceived Dyspnea (scale 0-10) of 3 or higher
3. Severe patient baseline hypercarbia/hypercapnia of 50mmHg or higher as measured by TcCo2 or arterial or venous blood gas

Exclusion Criteria

1. Patient has unstable cardiovascular condition
2. Significant nasal occlusion either unilateral or bilateral
3. Inability to provide informed consent
4. Pregnancy

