patient and clinician perception assessment scores. The baseline characterization for Phase 1 will provide patient background, history, and initial clinical evaluation. For Phase 2, baseline characterization will only include the initial clinical evaluation as no further initial evaluation is warranted. An acclimatization period is not necessary for Phase 2, as both devices will have been calibrated in Phase 1, requiring only a cannula change. Titration of therapy (Flow/FiO2) is only expected during Phase 1 (or in the event the patient decompensates and requires adjustment), as this study is a comparison of device efficacy. For the therapeutic characterization segment of each phase, final patient data for the corresponding device design will be recorded. Following this, the clinician and the patient will complete VAS perception scores corresponding to each device design. Primary and secondary outcomes will be evaluated and recorded upon the completion of all study phases. Tertiary outcomes will be evaluated and recorded upon the completion of each study phase.

This study will be conducted in an inpatient or outpatient hospital setting where patient testing can be performed with appropriate medical supervision and staff training to maintain patient safety. All respiratory interventions will be tracked within the study window for each patient.

V. Subject Enrollment

Subjects will be recruited by investigators using patient medical records and initial patient contact. Subjects will be consented prior to participation in this study (Aims 1-3). Once consented, the participants and investigators will complete data collection in all Aims during the trial period. Subjects have the right to withdraw consent to participate in this study at any time, for any reason.

Sample Size:

To provide a sufficiently powered sample dataset, we will enroll up to 32 subjects to complete this study on designs, with a calculated sample size of N=26 plus a 20% failure/fallout rate. This will provide sufficient data to adequately inform on the study objectives.

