This sample size was estimated through use of references that (1) approximated minimal clinical important difference of dyspnea (modified Borg scale) and (2) approximated expected standard deviation of prior datasets measuring dyspnea.¹⁶⁻¹⁸ Estimated minimal clinical important difference of dyspnea was determined to be a difference value of 2 in modified Borg for dyspnea.¹⁶ In reviewing publications from Roca 2010 and Schwabbauer 2014, it was estimated that a value of 2 to 3 was suitable for the standard deviation of dyspnea for the modified Borg scale. Therefore, for this study, using the paired t-test sample size calculation, with an expected difference of 2, and an expected standard deviation of 3, using a desired power of 90% with alpha=0.05, the sample size is estimated at 26 to show if the data may or may not have any difference.

Vapotherm, Inc

New HVNI Device Design Efficacy in Relieving Dyspnea

Confidential

VI. Study Procedures

This validation study is non-blinded to investigators and patients by necessity, as there is a distinct difference in size and appearance between the Precision Flow and HVT2.0 HVNI device designs. However, patients may not know the difference between conventional and new device design. This study is a crossover design trial that will measure, ventilation, comfort, and efficacy—specifically the effect of relief of dyspnea as demonstrated by RPD assessment and measured by TcPCO₂ device. In addition, patient physiologic outcomes (e.g. HR, RR, BP, SpO₂), as well as patient & clinician assessment scores will be evaluated and recorded. Figure 1 illustrates a flowchart of overall study procedures.

Screening, Enrollment, & Management

During screening, subjects will be asked to participate in this study, and if so, they will provide informed consent prior to enrollment. Subjects will be instructed that if at any time during the study that they wish to discontinue the study, they are free to stop the testing and discontinue study participation at any time. All study procedures will be explained to the subject prior to starting any procedures, and all participants will be given a copy of the informed consent form.

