- Clinician perception of Monitoring and support of therapy required (adjustments, refilling fluids, adjusting interface), ranging from Minimal to Frequent, as continuous VAS.

VIII. Statistical Analysis

Baseline patient demographics and characteristics will be summarized, compared, and appropriate statistical testing will be performed for the continuous and categorical variables. Assuming a non-normal data distribution for this crossover order-randomized study design, the non-parametric Wilcoxon Signed Rank Sum test will be performed with significance interval of 0.05 on all applicable variables. Parametric analytical analogues (e.g. t-test) will be use if the measurements present a normal distribution. Otherwise, for the categorical variables, the Fisher's Exact test will be performed. Data will be compared and graphed accordingly for a visual comparison with accompanied statistical notations.

IX. Risks and Discomforts

This validation study does not present significant risk to patients, as supplemental oxygen is routinely provided to patients as a standard practice in hospitals¹⁹. Use of high flow nasal cannula (HFNC) therapy has no known risks and has been used in clinical settings for approximately 17 years. Additionally, there are no known reports of adverse events related to the administration of high nasal flows when the gas has been appropriately conditioned to near body temperature and fully humidified. Existing literature indicates that approximately only 4 cmH₂O of distending pressure may be generated in the upper airway, which is well below any known threshold for injury.^{20,21} Furthermore, it has been demonstrated that delivery of high flows of conditioned gas from a nasal cannula has a positive effect on airway mucosal function.^{22,23} The patients enrolled in this study will be closely monitored as part of standard medical practice.

For these reasons, we have determined that this study represents non-significant risk to the subjects. The high flow nasal cannula system used has no known risk and has been used in hospitals for approximately 17 years. During both study phases, patients will be closely monitored as part of the normal care. Patients may experience mild discomfort from a cannula in contact with their nose, face or around their ears and possibly a runny nose from the humidity contained in the gas flow.

X. Potential Benefits

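### All endpoints are tested at 0.05 and collectively carry the equivalence claim, with no rule for which decides; identical devices would show at least one chance difference in roughly 35–50% of trials

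*Combined protocol and SAP*

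**What the plan says.** Section VIII (Statistical Analysis) sets one rule for everything measured: "the non-parametric Wilcoxon Signed Rank Sum test will be performed with significance interval of 0.05 on all applicable variables". A t-test replaces the signed-rank test where data look normal, and Fisher's exact test is used for categorical variables. The section gives no order of testing, no adjustment and no statement of which result decides.

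Section II (Overall Study Objective) ranks the endpoints. On the first aim it states: "The primary endpoint is the patient's targeted relief of dyspnea, as measured by the modified Borg". Heart rate, respiratory rate, blood pressure, SpO2 and TcPCO2 are secondary, and two patient and five clinician perception scores are tertiary. The same section then says that the endpoints "described will establish equivalence of outcomes between Precision Flow HVNI and HVT2.0 HVNI device design". It gives no margin and no rule for combining endpoints.

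Section V (Sample Size) considers RPD only, "with an expected difference of 2, and an expected standard deviation of 3".

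Section VII (Data Collection) states: "For each segment of each phase, the following data will be recorded for comparison". Section VIII does not say which segment is compared. Section IV (Study Design) places each device's final data in Therapeutic Characterization.

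**The concern.** The ranking in Section II has no consequence in Section VIII. The endpoint that sized the trial is tested in the same way, and at the same level, as diastolic pressure or a clinician ease-of-use score. Section II then refers to the endpoints in the plural when it speaks of equivalence.

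With 13 or 14 unadjusted difference tests, two identical devices will often show at least one nominally significant difference. The plan does not say how such a result bears on the equivalence statement. The hypothesis in Section II also has two parts, dyspnea relief and ventilation. The second depends on TcPCO2, which has no defined part in the decision. If this is left open, the weight given to a stray significant result, or to TcPCO2, would be argued after the data are seen.

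**Working it through.** **Reproducing the plan's own figure.** Section V gives a difference of 2, SD 3, power 90% and alpha 0.05 for a paired t-test.
- Standardised difference: 2/3 = 0.667.
- Exact two-sided power from the noncentral t distribution: 89.2% at n = 25 and 90.4% at n = 26. The stated 26 reproduces.
- Enrolment: 26 × 1.2 = 31.2, rounded up to 32, as stated.

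This calculation covers one endpoint, RPD, and one test at 0.05. No other endpoint has a stated difference, SD or power.

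**Counting the device comparisons at the therapeutic reading.**
- Primary: RPD, 1.
- Secondary: heart rate, respiratory rate, SpO2, TcPCO2 and blood pressure. That is 5 with blood pressure as one item, as the endpoint lists have it, or 6 if systolic and diastolic are tested separately, as the Glossary definition would allow.
- Tertiary: 2 patient and 5 clinician VAS scores, 7.
- Total: 1 + 5 + 7 = 13, or 1 + 6 + 7 = 14.

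**Chance of at least one p<0.05 with no true difference, independent tests:** 1 − 0.95^k.
- k = 13: 1 − 0.95^13 = 48.7%.
- k = 14: 1 − 0.95^14 = 51.2%.
- Primary plus secondary only: k = 6, 26.5%; k = 7, 30.2%.
- RPD alone: 5%.

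**Allowing for correlation.** All endpoints come from the same patients and several overlap: RPD with patient-rated relief, patient-rated with clinician-rated comfort, systolic with diastolic pressure. The documents give no correlations, so a common correlation ρ among the within-patient differences is an assumption. Simulated signed-rank tests (26 pairs, normally distributed differences, 20,000 trials per setting) give:

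| Comparisons | Independent (formula) | ρ = 0.1 | ρ = 0.3 | ρ = 0.5 | ρ = 0.7 |
|---|---|---|---|---|---|
| 13 | 48.7% | 47.5% | 42.0% | 34.5% | 25.3% |
| 14 | 51.2% | 50.3% | 44.2% | 35.9% | 26.4% |
| 6 | 26.5% | – | 24.0% | 21.1% | – |
| 7 | 30.2% | – | 27.5% | 23.3% | – |

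Paired t-tests in the same simulation for 13 and 14 comparisons agree to within about 1.5 percentage points. These figures cover one reading per device.

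**The case against.** The strongest reply is that the plan does have a hierarchy. RPD is the single named primary endpoint, it alone sized the trial, and its own false-difference risk is 5% whatever happens elsewhere. A common alpha does not make every endpoint equally important, and half or more of the comparisons (7 of 13 or 14) are tertiary scores. This stands. A reader might infer that the sponsor is free to pick afterwards which endpoints count, but the prespecified primary limits that. What stays open is how far the other endpoints bear on the equivalence statement in Section II.

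A reader might also infer that one chance finding on a minor variable overturns equivalence. No passage says so, and none says that all endpoints must agree.

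The error also runs against the sponsor. The aim is comparability, so a false difference weakens the claim and does not produce a false one. If the plan did require every endpoint to meet an equivalence criterion, no alpha adjustment would be needed and the cost would be power. This stands too.

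Two smaller points hold. The trial is unblinded and the devices look different, so a difference in clinician ease-of-use scores may be real. The case for extra multiplicity from other segments is also weak: acclimatization takes place only in Phase 1, so it offers no within-patient device pair.

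The reply does not remove the gap. Section VIII still tests everything at 0.05, Section II still speaks of the endpoints jointly, and dropping all the VAS scores still leaves a 21–30% chance of a stray difference.

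**Conclusion.** The point holds as a missing decision rule. With identical devices and 13–14 comparisons, the chance of at least one nominally significant difference is 49–51% under independence, about 42–44% at ρ = 0.3 and about 35–36% at ρ = 0.5. It falls to about a quarter at ρ = 0.7. An even chance is therefore the upper end of the range for a single reading, not the expected value. The results assume one reading per device, a common correlation that the documents do not supply, and continuous differences without the ties that Borg scores will produce.

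The documents do not support reading this as a route to a false equivalence claim, because chance differences push the other way. The related and more serious gap is that Section VIII uses difference tests with no margin, so that a non-significant result could be taken as equivalence. Naming the deciding endpoint without also giving it a margin would not repair the claim. The two belong in one change, made before any data are seen.

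**What to change.** In Section VIII:

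1. State that RPD at Therapeutic Characterization is the deciding endpoint. Equivalence is concluded if the confidence interval for the paired device difference, at a stated level, lies wholly within a prespecified and justified margin. A result of p>0.05 is not the criterion.
2. State that TcPCO2 at the same reading is assessed next, with its own prespecified margin, and only if RPD meets its criterion. The fixed sequence needs no split of alpha, and it covers the ventilation part of the hypothesis.
3. Report heart rate, respiratory rate, blood pressure, SpO2 and all VAS scores as device differences with 95% confidence intervals, without significance statements.

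In Section II, rest equivalence on the deciding endpoint or endpoints, not on the endpoints generally.

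A Bonferroni level (0.05/13 = 0.0038 or 0.05/14 = 0.0036) for the existing difference tests is not a substitute. It would make non-significance easier to reach, which helps only if non-significance is misread as equivalence.

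The cost is mostly wording, with no extra visits or measurements. The trial gives up confirmatory statements on heart rate, respiratory rate, blood pressure, SpO2 and the VAS scores, none of which it was sized for. The documents give no margin, so the sponsor must justify both. The 26 patients were calculated to detect a difference, so that number must be checked against the chosen margins.
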